8.3 Causality

Using the following criteria, the relationship of the AE to the study drug should be assessed as follows:

Yes: The event is suspected to be related if:

- there is a clinically plausible time sequence between onset of the AE and administration of study treatment; and/or
- there is a biologically plausible mechanism for the study treatment to cause or contribute to the AE; and/or
- the event responds to withdrawal of the study medication (dechallenge) and/or recurs with rechallenge (when clinically feasible); and/or
- the AE cannot be reasonably attributed to concurrent/underlying illness, other drugs, or procedures

No:

- the AE is more likely to be explained by the subject's clinical state, underlying disease, concomitant medication, study or non-study procedure; and/or
- the time of occurrence of the AE is not reasonably related to administration of study treatment; and/or
- the event is unlikely to be related to the investigational product(s)

In the event of a possible drug-related AE, the investigator should reasonably attempt to assess its relationship to Pomalidomide and dexamethasone.

8.4 Adverse events reporting procedures

All AEs (eg, any new event or worsening in severity or frequency of a preexisting condition or laboratory finding) for randomized subjects with an onset date after the subject signs consent for study participation must be promptly documented on the AE CRF. Details of the event must include severity, relationship to study drug, duration, action taken, and outcome. Non-serious AEs will not be recorded for subjects who screen fail. All SAEs will be recorded from the time of informed consent in the CRF for all subjects.

All AEs for randomized subjects will be collected from the time the subject signs informed consent through PD. In addition, the Investigator should report any AE that may occur after this time period that is believed to have a reasonable possibility of being associated with study drug. All AEs that are considered related to study drug must be followed to resolution or stabilization if improvement is not expected.

Adverse events which completely resolve and then recur should be recorded as a new AE. For the OS phase, a follow up of ongoing AEs should be attempted by telephone, and documented in the subject's source file. The Principal Investigator is responsible for evaluating all AEs, obtaining supporting documents, and determining that documentation of the event is adequate. Laboratory abnormalities should be recorded as AEs on the CRF only if they require treatment or are otherwise considered clinically significant by the Investigator.

All deaths during PFS phase are to be reported as SAEs.

The corresponding entry for progression-related deaths on the AE CRF should use the verbatim term “Disease Progression” rather than the specific sign or symptom that may have been the immediate cause of death. Additional details of the event (such as the primary and contributory causes of death) should be reported on the Death CRF.

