7.2 Response assessment

Starting from the second Cycle, response will be evaluated by the investigators according to the EBMT criteria, using results from central site laboratories, at every Day 1 of every cycle until PD (PFS phase). All treatment discontinuation decisions will be made by treating physicians based on the central laboratory results. In the Long-term follow-up phase (OS phase) subjects will be contacted every 2 months for 2 years after the randomization of the last subject. Survival time, cause of death and any subsequent anti-MM treatments should be recorded on CRFs.

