8.5 Serious adverse events definitions

An SAE is one that meets one or more of the following criteria:

- Death
- Life-threatening experience defined as any adverse experience that places the subject, in the view of the Investigator, at immediate risk of death at the time of occurrence; ie, it does not include a reaction that, had it occurred in a more severe form, might have caused death.
- Requires inpatient hospitalization or prolongation of an existing hospitalization (except scheduled hospitalizations for a non-acute, unrelated cause such as an elective surgery)
- Results in persistent or significant disability/incapacity
- Is a congenital anomaly/birth defect in the offspring of an exposed subject
- Important medical events that may not result in death, be life threatening, or require hospitalization, may be considered an SAE when, based upon appropriate medical judgment, it jeopardizes the subject and may require medical or surgical intervention to prevent one of the outcomes listed in this definition.

Any death occurring within 30 days of the subject receiving study drug—regardless of the subject having discontinued from the study—must be reported to the sponsor as an SAE.

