8.6 Serious adverse event reporting and documentation requirements

The Sponsor must be notified of the occurrence of any SAE within 24 hours of the Investigator, designee, or site personnel’s knowledge of the event. To report an SAE, the site representative must complete an SAE form in English and submit to the sponsor as instructed in the separate study manual.

Follow-up reports must be submitted in a timely fashion as additional information becomes available.

The Investigator is responsible for notifying the IRB or IEC in accordance with local regulations, of all SAEs. The sponsor may request additional source documentation pertaining to the SAE to be sent to the Sponsor. If a subject is permanently withdrawn from the study because of a SAE, this information must be included in the initial or follow-up SAE report form as well as the CRF.

The sponsor is responsible for notifying the appropriate global Health Authorities, when required, and in accordance with applicable laws and regulations.

All SAEs occurring from the time that the subject signs consent for study participation through 30 days after the last administered dose of study drug or initiation of new anticancer therapy (whichever occurs first) must be reported. All SAEs regardless of relationship to study drug must be followed to resolution or to stabilization if improvement or resolution is not expected.

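### Sections 8.4, 8.5 and 8.6 end AE, SAE and death reporting at different points, and routine collection of non-serious AEs closes at PD with no post-dose tail

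*Protocol*

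**What the plan says.** Section 8.4 gives the routine window: "All AEs for randomized subjects will be collected from the time the subject signs informed consent through PD". It continues: "In addition, the Investigator should report any AE that may occur after this time period that is believed to have a reasonable possibility" of a link with study drug. For events still open at that stage: "For the OS phase, a follow up of ongoing AEs should be attempted by telephone, and documented in the subject's source file". On serious events the same section says "All SAEs will be recorded from the time of informed consent in the CRF for all subjects", with no end date, and "All deaths during PFS phase are to be reported as SAEs". Section 7.2 treats the PFS phase as the period up to PD.

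Section 8.5 adds a rule tied to dosing. "Any death occurring within 30 days of the subject receiving study drug" must be reported to the sponsor as an SAE, even if the subject has left the study.

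Section 8.6 sets the SAE window from consent "through 30 days after the last administered dose of study drug or initiation of new anticancer therapy (whichever occurs first) must be reported".

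Three other places matter. Section 7.3 requires two successive qualifying values for PD and dates it at the first. Section 4.1 keeps subjects who stop for toxicity under assessment until PD. Section 4.5 confirms that treatment assignment is not blinded.

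**The concern.** The three sections run on different clocks: PD in 8.4, 30 days after drug in 8.5, and 30 days after the last dose or new therapy in 8.6. A site that uses 8.6 to decide what to send would leave out deaths that 8.4 or 8.5 requires, and two sites could treat the same death differently.

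The second problem is the PD cut-off for non-serious AEs. Up to PD every AE is collected whatever its cause. After PD, a new non-serious AE enters the data only if the investigator, who knows the treatment, believes it may be drug-related. Because PD is backdated to the first qualifying value, the change can take effect while the subject may still be on treatment. At stake are consistent safety reporting and a full record of events shortly after dosing.

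**Working it through.** **1. The windows side by side.** Each case is read against the explicit end point in each section.

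| Case | 8.4 | 8.5 death rule | 8.6 window |
|---|---|---|---|
| (a) Death before PD, more than 30 days after last dose | Required | Outside | Outside |
| (b) Death after PD, within 30 days of last dose, new therapy already begun | Outside the death rule | Required | Outside |
| (c) Death after PD, within 30 days of last dose, no new therapy | Outside the death rule | Required | Inside |
| (d) Unrelated non-fatal SAE after PD, within 30 days of last dose, no new therapy | Outside the through-PD window | Not applicable | Inside |
| (e) Non-fatal SAE before PD, more than 30 days after last dose | Inside | Not applicable | Outside |
| (f) Unrelated new non-serious AE after PD, within 30 days of last dose | Outside | Not applicable | Not applicable |

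Deaths (a) and (b) are each required by one explicit window only. Event (f) is required by none. The sentence in 8.4 on recording SAEs from consent has no end date, so for (d) it clashes with the through-PD window, and for SAEs generally with the closed window in 8.6.

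**2. Are (a) and (b) foreseeable?** Yes. Section 4.1 creates subjects who are off drug and not progressed, which is the setting for (a). Section 7.2 asks for subsequent anti-myeloma treatments to be recorded, so new therapy after PD, the setting for (b), is expected.

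**3. Length of the uncovered stretch.** Inputs: 28-day cycles with assessment on Day 1 (Sections 4.3 and 7.2); last scheduled dose of a cycle on Day 22 for Pom/dex and Day 20 for DEX (Section 6.3); 30 days from 8.6. Visit tolerance, dose delays and early new therapy are ignored. PD is dated at a Day 1 visit, which is Day 29 of the cycle just ended.

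- Treatment stops at the first qualifying value. The last dose was 29 − 22 = 7 days earlier (Pom/dex) or 29 − 20 = 9 days earlier (DEX). The 30-day point falls 30 − 7 = 23 or 30 − 9 = 21 days after PD.
- Treatment runs one more cycle, to the confirming visit 28 days later. The last dose is 22 − 1 = 21 or 20 − 1 = 19 days after the PD date. The 30-day point falls 21 + 30 = 51 or 19 + 30 = 49 days after PD.

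Read literally, then, routine collection ends about 21 to 51 days before the point at which 8.6 stops asking for SAEs. The design median PFS is 2 months for DEX and 3 for Pom/dex (Section 9.4).

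**4. Does a 30-day tail change the comparison between arms?** Assume exponential PFS at the design medians, so λ = ln 2 / median = 0.3466 (DEX) and 0.2310 (Pom/dex) per month. Mean windows 1/λ are 2.89 and 4.33 months. Assume also a constant AE hazard h, equal in both arms; the protocol gives none, so h is ranged.

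- Through PD: P = h/(h + λ). At h = 0.1, 0.1/0.4466 = 22.4% against 0.1/0.3310 = 30.2%, a difference of 7.8 points. At h = 0.2, 36.6% against 46.4%, or 9.8 points. For h from 0.02 to 0.5 the difference is 2.5 to 10.1 points.
- Through PD plus 30 days (0.986 months, last dose taken at PD): P = 1 − [λ/(h + λ)]·exp(−0.986h). At h = 0.1, 29.7% against 36.8%, or 7.1 points. At h = 0.2, 47.9% against 56.0%, or 8.1 points.

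**The case against.** The strongest reply is that the rules add up. Section 8.6 says what must be reported and nowhere forbids reporting more. Death (a) is still required by 8.4 and death (b) by 8.5. Section 8.6 opens by asking for notification of any SAE within 24 hours, 8.5 lists death as an SAE criterion, and survival time and cause of death are recorded in long-term follow-up. This stands as far as it goes: a reader might infer that deaths escape reporting altogether, and the documents do not support that. But the additive reading is nowhere stated, and a closed window in the section on SAE reporting invites the narrower one.

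A reader might also infer that AE collection stops entirely at PD. It does not. Possibly related AEs, SAEs inside the 8.6 window and telephone follow-up of ongoing AEs all continue. What drops out is narrow: new, non-serious events judged unrelated.

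A third inference is that AE rates cannot be compared between arms, and that a tail would cure this. Neither is supported. Treatment itself runs to PD or unacceptable toxicity, so exposure differs whenever PFS differs. The illustration shows a 30-day tail moving the crude difference only from 7.8 to 7.1 points, or from 9.8 to 8.1. Exposure-adjusted rates may be in the SAP, which is not at hand, so their absence is not part of this point.

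Finally, since treatment also ends at PD, stopping routine collection there can be called a design preference. That answer is incomplete: PD is dated before it is confirmed, and 8.6 itself treats the 30 days after dosing as relevant to safety.

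**Conclusion.** The point holds in two parts. First, 8.4, 8.5 and 8.6 set end points that disagree, leaving two foreseeable kinds of death outside the 8.6 window although another section requires them. This rests on the text alone. Second, ending causality-independent collection of non-serious AEs at a backdated PD is a weak rule: it can close before confirmation, leaves no post-dose tail, and makes later capture depend on an open-label judgement.

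The gap of about 21 to 51 days assumes dosing and visits on schedule and no new therapy within 30 days of the last dose. It is calendar time, not a count of lost events or a bias, and the protocol offers no figure from which either could be derived. The correction is worth making because the duties conflict and the remedy is cheap.

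**What to change.** - Reconcile 8.4, 8.5 and 8.6 into one rule that states start and end for AEs, SAEs and deaths, applied identically in both arms.
- State in 8.6 that its new-therapy and 30-day cut-offs do not override the death rules of 8.4 and 8.5.
- Run routine AE collection at least to the post-last-dose point 8.6 already uses for SAEs instead of ending it at PD. Do not shorten it for subjects who stop for toxicity and reach PD later.
- Where PD remains a reference point, say whether the first or the confirming date is meant.
- So that the clock is the same in both arms, say which drug starts it in the DEX arm: Section 6.1 classes dexamethasone as non-investigational, and Section 6.5 names only pomalidomide and low-dose dexamethasone as study drugs. Section 5.4, which withdraws subjects from the study at progression, must also be reconciled with any reporting after PD.

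The cost is a text amendment and up to about one more month of AE collection per subject after treatment ends. Time between a first PD value and its confirmation falls between visits already planned. Long-term follow-up contacts are every 2 months, so one extra contact may be needed.

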8.5 Serious adverse events definitions

An SAE is one that meets one or more of the following criteria:

- Death
- Life-threatening experience defined as any adverse experience that places the subject, in the view of the Investigator, at immediate risk of death at the time of occurrence; ie, it does not include a reaction that, had it occurred in a more severe form, might have caused death.
- Requires inpatient hospitalization or prolongation of an existing hospitalization (except scheduled hospitalizations for a non-acute, unrelated cause such as an elective surgery)
- Results in persistent or significant disability/incapacity
- Is a congenital anomaly/birth defect in the offspring of an exposed subject
- Important medical events that may not result in death, be life threatening, or require hospitalization, may be considered an SAE when, based upon appropriate medical judgment, it jeopardizes the subject and may require medical or surgical intervention to prevent one of the outcomes listed in this definition.

Any death occurring within 30 days of the subject receiving study drug—regardless of the subject having discontinued from the study—must be reported to the sponsor as an SAE.

8.6 Serious adverse event reporting and documentation requirements

The Sponsor must be notified of the occurrence of any SAE within 24 hours of the Investigator, designee, or site personnel’s knowledge of the event. To report an SAE, the site representative must complete an SAE form in English and submit to the sponsor as instructed in the separate study manual.

Follow-up reports must be submitted in a timely fashion as additional information becomes available.

The Investigator is responsible for notifying the IRB or IEC in accordance with local regulations, of all SAEs. The sponsor may request additional source documentation pertaining to the SAE to be sent to the Sponsor. If a subject is permanently withdrawn from the study because of a SAE, this information must be included in the initial or follow-up SAE report form as well as the CRF.

The sponsor is responsible for notifying the appropriate global Health Authorities, when required, and in accordance with applicable laws and regulations.

All SAEs occurring from the time that the subject signs consent for study participation through 30 days after the last administered dose of study drug or initiation of new anticancer therapy (whichever occurs first) must be reported. All SAEs regardless of relationship to study drug must be followed to resolution or to stabilization if improvement or resolution is not expected.

9. STATISTICAL METHODS

This section outlines the statistical analysis strategy and procedures for the study

9.1 Sample size determination

Approximately 250 subjects will be enrolled (1:1 randomization) in order to show a 40% increase in median PFS (from 50% median PFS after 2 months in the control arm to 70% in the interventional arm) with a statistical power of 90% and the two-sided statistical significance level at 0.05.

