5. SUBJECT SELECTION AND WITHDRAWAL

5.1 Number of subjects and study sites.

Approximately 250 subjects will be enrolled (125 in each arm), in 20 different sites in North America and Europe.

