9.4 Primary Efficacy Analysis

The primary analysis of PFS, will be to compare the two randomized arms via a two-sided, log-rank test stratified by β_2 microglobulin levels ($<$ vs ≥ 3 mg/L), prior lines of anti-MM treatment (3 vs >3) and subjects' age (\leq vs >75 years).

Further analysis of PFS will include the computation of hazard ratios and estimation of PFS functions.

The PFS hazard ratio of Pom/dex to DEX will be computed using a stratified Cox proportional hazards model with treatment arm as the sole covariate. The PFS functions for each randomized arm will be estimated using the Kaplan-Meier product-limit method.

Two-sided, 95% confidence intervals for median PFS will be computed by randomized arm. PFS rates at 1, 2, 3, 6 and 12 months will be estimated from the Kaplan-Meier curve. Each analysis will be performed after all subjects had been followed for the given time point estimate (ie, the 2-month PFS rate estimate will be estimated when all subjects have been followed for a minimum of 2 months).

A total of 125 progression events will provide 90% power to detect, with a 1-sided significance level of 0.025, a 50% increase in median PFS for the Pom/dex arm vs the DEX arm (3 vs 2 months, respectively).

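### Section 9.1 sizes the trial on 50% versus 70% progression-free at 2 months, mislabels this a 40% increase in median PFS, and conflicts with the 3 versus 2 months of sections 1.7 and 9.4

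*Protocol*

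**What the plan says.** The protocol states a powered target effect for PFS in two different ways.

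- **Section 9.1** sets the sample size. It plans about 250 subjects with equal allocation and gives the purpose as "in order to show a 40% increase in median PFS (from 50% median PFS after 2 months in the control arm to 70" (this last figure is also a percentage and belongs to Pom/dex). Power is put at 90% and alpha at two-sided 0.05.
- **Section 9.4**, repeated in section 1.7, works from events. The effect there is "a 50% increase in median PFS for the Pom/dex arm vs the DEX arm (3 vs 2 months, respectively". The power claim attached to that effect reads: "A total of 125 progression events will provide 90% power to detect, with a 1-sided significance level of 0.025".

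Section 5.1 gives the split as follows: "Approximately 250 subjects will be enrolled (125 in each arm". Section 4.1 repeats about 250 subjects and says that about 125 progression events are needed. Section 9.4 names the primary test as a two-sided log-rank test stratified by the randomization factors. Nothing in the protocol connects the effect in 9.1 with the one in 1.7 and 9.4.

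**The concern.** A median PFS is a time. The 50% and 70% in section 9.1 are proportions of subjects still progression-free at 2 months, so the 40% is a relative rise in a 2-month rate under the wrong name. This can be seen without any assumption about the shape of the PFS curve.

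The two statements describe different effects, and each carries a 90% power claim. A reader, ethics committee or data monitoring committee cannot tell which effect the trial is built to detect. The sample size also appears to come from a comparison of proportions, which is not the planned primary analysis. What is at stake is the stated power for the primary endpoint and the number of events at which PFS will be analysed.

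**Working it through.** **Inputs.** 250 subjects, 125 per arm (9.1, 5.1); 50% versus 70% at 2 months, 90% power, two-sided 0.05 (9.1); medians 3 versus 2 months, 125 events, 90% power, one-sided 0.025 (1.7, 9.4); 125 events (4.1). Two-sided 0.05 and one-sided 0.025 use the same critical value, 1.960, so alpha is not part of the conflict. The 90% power quantile is 1.2816.

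**Step 1: reproduce the 250.** Two proportions, pooled variance, no continuity correction, mean proportion 0.60:

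n per arm = [1.960·√(2·0.60·0.40) + 1.2816·√(0.50·0.50 + 0.70·0.30)]² / (0.70 − 0.50)² = (1.358 + 0.869)² / 0.04 ≈ 124.

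That is 248 in total, in line with about 250. Power with 125 per arm is 90.2%. Unpooled variance gives 121 per arm and the arcsine method about 124 to 125. With continuity correction it is 134 per arm (268), which does not match.

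**Step 2: put the effects on one scale.** Assume exponential PFS with a control median of 2 months.

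- 50% to 70% at 2 months: HR = ln 0.70 / ln 0.50 = 0.515; median = 2/0.515 = 3.89 months, an increase of 94%.
- 3 versus 2 months: HR = 2/3 = 0.667; proportion progression-free at 2 months = 0.5^(2/3) = 63%, not 70%.
- For comparison, a literal 40% increase in median would be 2.8 months: HR = 1/1.4 = 0.714, with 61% progression-free at 2 months.

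So the figures in 9.1 match neither their own label nor the target in 1.7 and 9.4.

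**Step 3: events for 90% power with the log-rank test.** Schoenfeld, 1:1 allocation: d = 4·(1.960 + 1.2816)² / (ln HR)² = 42.03 / (ln HR)².

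| Effect | HR | Events, Schoenfeld | Events, Freedman |
|---|---|---|---|
| 50% to 70% at 2 months | 0.515 | 96 | 103 |
| 3 versus 2 months | 0.667 | 256 | 263 |

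**Step 4: power at 125 events.** Power = Φ(√d·|ln HR|/2 − 1.960).

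- HR 0.667: Φ(11.18·0.4055/2 − 1.960) = Φ(0.307) = 62% (Freedman 61%).
- HR 0.515: 96% (Freedman 95%).

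Neither effect gives 125 events as the requirement for 90% power.

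**Step 5: power for 3 versus 2 months at higher event counts,** same formula.

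| Events | Power |
|---|---|
| 200 | 82% |
| 225 | 86% |
| 240 | 88% |
| 250 | 89% |

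**The case against.** The strongest reply is that 250 subjects are nearly enough for 3 versus 2 months. The log-rank test has 88% to 89% power at that effect once 240 to 250 events are in, and with medians of 2 to 3 months most subjects should have an event. This stands. A reader might infer that 250 subjects and 90% power hold only for a much larger effect. The documents do not support that for the planned test. The shortfall lies in the 125 events, not in the number of subjects.

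Three further readings go too far.

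- **Three powered targets.** The 40% in 9.1 is a wrong label for 50% to 70%, since 0.70/0.50 = 1.40. It is not a separate effect with its own power claim. There are two effects and two claims.
- **The origin of 250 is certain.** The two-proportion calculation fits both the figures in 9.1 and the result, but the protocol does not name its method, and 256 events for 3 versus 2 months is also close to 250. Likewise, 125 events equals the number per arm, but that one was copied from the other would be a guess.
- **A negative result would be uninterpretable.** Section 9.4 still provides a hazard ratio, Kaplan-Meier curves and confidence intervals for the medians.

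It can also be objected that the hazard ratios rest on an exponential model that the protocol does not state. That affects the sizes in steps 2 to 5. It does not affect the mislabel.

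**Conclusion.** The point holds. Section 9.1 misdescribes its own figures and contradicts sections 1.7 and 9.4 on the primary endpoint, and no other section resolves this. On the hazard-ratio scale the two targets are 0.515 and 0.667, and they need about 96 and 256 events for 90% power. If 3 versus 2 months is the real target, the planned 125 events give about 62% power, not 90%.

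This assumes exponential PFS with a control median of 2 months, proportional hazards, no allowance for stratification, and 125 read as the total number of PFS events. The protocol calls them progression events although deaths also count towards PFS. Any deaths on top would raise the power, but 256 events cannot be reached with 250 subjects. The documents do not say which of the two effects governs, so that choice is the sponsor's.

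**What to change.** 1. State one target effect, as a hazard ratio or a pair of medians, and use it in 1.7, 9.1 and 9.4. Delete from 9.1 both the claim of a 40% increase in the median and the 50%-to-70% basis.
2. If 3 versus 2 months is kept, base 9.1 on the log-rank test at HR 0.667 and two-sided 0.05, and give the same event count in 1.7, 4.1, 9.1 and 9.4. There are two ways to do this:
   - keep 125 events and state about 62% power; or
   - keep 250 subjects, run the PFS analysis at a higher event count and state its power from step 5. The number reached depends on follow-up and dropout, which the protocol does not give, so the chosen count needs its assumptions beside it.

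Rewriting 9.1 alone would leave two event targets in the protocol.

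**Cost.** Either the stated power becomes less favourable or the PFS analysis comes later. The number of subjects does not change.
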